## **8.7. Other Assessments of Drug Effect**

### **8.7.1. Sheehan Disability Scale**

The SDS instrument is patient rated with the first 3 items in a numeric rating scale and the last 2 questions asking for number of days impacted ([Sheehan et al, 1996](#); [Sheehan, 1983](#)). The first 3 items, one for each of the 3 domains, are rated on an 11-point numeric rating scale ranging from 0 (not at all), 1 to 3 (mildly), 4 to 6 (moderately), 7 to 9 (markedly), to 10 (very severely). The sum score from the first 3 items, ranging from 0 (unimpaired) to 30 (highly impaired), will be used to evaluate global functional impairment. Individual subscores from the first 3 items will also be reported to assess the impact of panic disorder on work, social life/leisure activities, and family life/home responsibilities.

Two additional items measuring “days lost” and “days unproductive” during the last week further quantify the lost and reduced productivity in school or work.

### **8.7.2. Hamilton Anxiety Rating Scale**

The HAM-A is a clinician interview–administered scale designed to measure the signs and symptoms of anxiety states in an adult population. It has 14 items and a recall period of the past week. There are 2 domains covered within the questionnaire, a Somatic factor (made up of 8 items) and a Psychic factor (made up of 6 items). A total score (ranging from 0 to 56) can be calculated in addition to the 2-dimension scores. Lower scores indicate less anxiety.

### **8.7.3. European Quality of Life**

The EQ-5D-5L is a generic estimate of health status with 2 parts ([EQ-5D-5L User Guide, 2019](#)). The first part, the descriptive system, was designed to assess decrement of health in terms of 5 domains: mobility, self-care, usual activities, pain/discomfort, and anxiety/depression. Each of these dimensions has a self-rated 5 level response: no problem (level 1), slight problems (level 2), moderate problems (level 3), severe problems (level 4), and unable to/extreme problems (level 5). Thus, a health profile consisting of a 5-digit code based on respondent’s selected levels for each of the 5 dimensions will be generated. For example, a respondent with a health profile code of 12345 would have no problem with mobility, slight problems with self-care, moderate problems with usual activities, severe problems with pain/discomfort, and extreme problems with anxiety/depression. Based on this 5-digit profile, a single summative index value can be computed according to the preferences of the general population of a given count/region. The second part of EQ-5D-5L is the EQ Visual Analog Scale (EQ VAS), a self-rated vertical visual analog scale with the top endpoint labeled as “The best health you can imagine” and the bottom endpoint labeled “The worst health you can imagine.” This scale takes

a single numeric number between 0 and 100 to represent a respondent's own rating of overall health today.

## 9. STATISTICAL CONSIDERATIONS

### 9.1. Statistical Hypotheses

The hypotheses of interest for the efficacy endpoints are 2-sided tests of superiority comparing the darigabat (DAR) with placebo.

$$H_0: \mu_{\text{placebo}} = \mu_{\text{DAR}} \text{ vs } H_1: \mu_{\text{placebo}} \neq \mu_{\text{DAR}}$$

#### 9.1.1. Multiplicity Adjustment

The hypothesis tests will be conducted in a hierarchical order from the primary efficacy endpoint to the secondary endpoints each at a 2-sided a level of 0.05. Specifically, if the primary hypothesis test on proportion of participants free of panic attacks as assessed by participant daily eDiary during the last 2 weeks of the Maintenance Treatment Period is successful, the key secondary endpoint of change from Baseline in PDSS total score at Week 14 will be similarly tested at a level of 0.05. If the second test is successful, the hypothesis on change from baseline in panic attack frequency during the last 2 weeks of the Maintenance Treatment Period will be conducted at a level of 0.05. The overall type I error rate in the family of the primary and key secondary efficacy endpoints thus is maintained at the 0.05 level.

### 9.2. Analysis Sets

The analysis sets that are defined for this trial are described in [Table 7](#).

**Table 7: Analysis Set Descriptions**

Term	Description	Analysis
ITT	All randomized participants.	Demographic and Baseline Characteristics
Safety Analysis Set	All randomized participants, who receive at least 1 dose of IMP. This will be the safety analysis set.	Safety analysis
FAS	Panic Attack Endpoints All randomized participants who receive at least 1 dose of IMP and have valid baseline panic attack assessments and have recorded all baseline/post-baseline panic attack assessments in an eDiary that requires collection of reports contemporaneous to the day being assessed and collection of the presence/absence of each associated symptom. Participants who have not met all inclusion/exclusion criteria but are randomized in error will not be included.	All efficacy analysis (including primary) related to panic attack events captured by eDiary
	Non-Panic Attack Endpoints All randomized participants who receive at least 1 dose of IMP and have valid baseline panic attack assessments. Participants who have not met all inclusion/exclusion criteria but are randomized in error will not be included.	All other efficacy analysis
PK Analysis Set	All randomized participants who receive at least 1 dose of IMP and have at least 1 measurable darigabat concentration.	PK analysis

Abbreviations: FAS=full analysis set; IMP=investigational medicinal product; ITT=intent-to-treat; PK=pharmacokinetic.

## 9.3. Statistical Analyses

### 9.3.1. General Considerations

Descriptive statistical methods will be used to summarize the data from this trial, with statistical testing performed for the efficacy endpoints. All statistical analyses will be conducted with the SAS® System, version 9.4 or higher. The remainder of this section is a summary of the planned statistical analyses of the primary and secondary endpoints as well as a description of planned safety analyses. Full details of these analyses will be included in the SAP.

### 9.3.2. Primary Endpoint/Estimand Analyses

The primary estimand has the following attributes:

1. Treatments as randomized
2. The population defined by the inclusion/exclusion criteria of the trial as the primary population of interest

3. The proportion of participants who are free of panic attacks during the last 2 weeks of the Maintenance Treatment Period as the primary endpoint of interest
4. The population level summary of interest is the estimated odds ratio of freedom from panic attack between treatments and the corresponding 95% CI
5. A composite strategy will be used to address missing values due to ICEs regardless of whether they are considered as treatment related. Specifically, participants who fail to achieve panic free in the last 2 weeks of treatment prior to ICE, including cases of missing all post-baseline assessments (other than for logistic reasons such as randomization errors) in the FAS defined in [Table 7](#), will be considered as failure.

The number and proportion of participants who are free of panic attacks during the last 2 weeks of the Maintenance Treatment Period will be summarized by visit and treatment group. The binomial repeated measures will be analyzed using the SAS® GLIMMIX procedure with logit link. The Baseline PDSS total score will be included as a covariate, and the treatment group, visits, evidence-based psychotherapy use, and interaction between treatment group and visit will be included as fixed effect. Model diagnostics will be performed to explore the goodness-of-fit. An unstructured covariance structure will be used for the repeated measures. If the unstructured covariance matrix results in convergence issue, a structured covariance matrix such as the heterogeneous Toeplitz structure may be used. In the case that a structured covariance matrix needs to be used, a robust sandwich variance estimator will be used. The odds ratio of active dose to placebo at the endpoint visit will be estimated based on the least squares mean difference in logit between the treatment groups from the GLIMMIX model with the associated 95% CI and p-values. A sensitivity analysis using Fisher's exact test and 95% exact CI will be performed to assess the robustness of the conclusion from the logistic regression and the impact of potential use of a structured covariance matrix on the estimation of treatment effect.

Additional sensitivity analyses will include all participants regardless of panic attack eDiary version used.

### **9.3.3. Secondary Endpoint/Estimand Analyses**

#### **9.3.3.1. Change From Baseline in PDSS Total Score at Week 14**

The first key secondary estimand has the following attributes:

1. Treatments as randomized
2. The population defined by the inclusion/exclusion criteria of the trial as the primary population of interest
3. The change from baseline in PDSS total score at Week 14 as the endpoint of interest
4. The population level summary of interest is the estimated treatment differences and the corresponding 95% CI based on an MMRM model
5. Missing values due to ICEs to be addressed by a hypothetical strategy followed by tipping point analyses

The change from Baseline to each trial visit in PDSS total score will be summarized by visit and treatment group. An MMRM analysis will be used with fixed effect of treatment group, visits, evidence-based psychotherapy use, and interaction between treatment group and visit. The baseline value of PDSS total score will be included as a covariate. Subject will be included as a random effect. An unstructured covariance structure will be used for the repeated measures. The Kenward-Roger approximation will be used to estimate the denominator degrees of freedom. If the unstructured covariance matrix results in convergence issue, the Fisher scoring algorithm may be used to obtain the initial values of covariance parameters. If convergence issues still cannot be resolved, a structured covariance matrix may be used with the heterogeneous Toeplitz covariance structure followed by the heterogeneous first-order autoregressive (AR[1]) structure. In the case that a structured covariance matrix needs to be used, a robust sandwich variance estimator will be used to address the potential adverse impact of covariance matrix misspecification. The difference between active dose and placebo at the endpoint visit will be estimated based on the least squares mean difference between the treatment groups at the endpoint visit from the MMRM with the associated 95% CI and p-values.

The following ICEs may be considered as treatment related and will be identified prior to database lock:

- Death
- Study/treatment discontinuation due to lack of efficacy
- Study/treatment discontinuation due to AEs
- Initiating evidence-based psychotherapy and continuing during double-blind treatment. Due to potential confounding effect, the observed data post ICE, if available, will be excluded.
- Initiating therapy with prohibited antidepressants or anxiolytics (eg, benzodiazepines, non-benzodiazepine anxiolytics including beta receptor antagonists) and continuing during double-blind treatment. Due to potential confounding effect, the observed data post ICE, if available, will be excluded.

For missing data due to ICEs where a treatment-related reason is identified, a pattern mixture model approach with varying level of shift parameters will be utilized. Specifically, a tipping point analysis will be performed to find a tipping point in the spectrum of shift parameter assumptions, at which the conclusion from the MMRM analysis changes. The individual cases of treatment-related ICEs will be pre-identified prior to database lock.

Further sensitivity tipping point analyses will be performed for all missing values following ICEs regardless of whether they are considered treatment related (including cases of missing all post-baseline assessments) to assess the robustness of the conclusion from the MMRM analysis.

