### **6.3. Measures to Minimize Bias: Randomization and Blinding**

#### **6.3.1. Participant Assignment to Treatment**

All participants will be centrally randomized in a 1:1 ratio to 1 of 2 treatment groups (placebo or darigabat 25 mg BID) at the Baseline Visit (Day -1) via an IRT according to a computer-generated randomization scheme. Participants will be sequentially assigned to the next available randomization number and will receive the IMP that corresponds to that randomization number. Once a randomization number has been assigned, it will not be reassigned.

The randomization will be stratified by evidence-based psychotherapy for the treatment of anxiety disorders including panic disorder with 2 strata: receiving evidence-based psychotherapy (initiated >3 months prior to the Screening Visit) or not receiving evidence-based psychotherapy (see [Section 4.1.1](#) for additional details).

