#### **9.3.4. Other Endpoints Analysis**

Analysis of proportion of participants free of panic attacks at other time points will also be based on the repeated measure logistic regression described in [Section 9.3.2](#). The PDSS total score at other time points will also be based on the MMRM model described in [Section 9.3.3.1](#). The frequency of panic attacks at other time points will be analyzed using the same methods described in [Section 9.3.3.2](#). Other endpoints, including change from baseline in CGI-S score, HAM-A scores, EQ-5D-5L, and SDS total score will be analyzed using similar MMRM models as described in [Section 9.3.3.1](#).

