### **9.5. Sample Size Determination**

A sample size of 114 participants per group (total of 228 participants) will provide at least 80% power to detect a difference of approximately 20% in proportion of participants (eg, 60% of darigabat group versus 40% of placebo group) free of panic attacks at Week 14 at  $\alpha=0.05$  (2-sided).

Two-hundred forty-six participants will be randomized to account for 18 participants whose panic attack assessments were made prior to implementation of protocol eDiary requirements (ie, assessments recorded contemporaneous to the day being assessed [minimizing any potential recall bias] and records of the presence as well as the absence of each DSM-5-TR panic attack symptom associated with a given panic attack [distinguishing between missing data and the absence of a specific symptom]).

In the event of higher than anticipated early terminations, Cerevel may extend enrollment to achieve trial objectives.

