5.12.1.2. Analytic Method

The change from Baseline to each trial visit in PDSS total score will be summarized by visit and treatment group. An MMRM analysis will be used with fixed effects of treatment group, visits, evidence-based psychotherapy use, and interaction between treatment group and visit. The baseline value of PDSS total score will be included as a covariate. Participant will be included as a random effect. An unstructured covariance structure will be used for the repeated measures. The Kenward-Roger approximation will be used to estimate the denominator degrees of freedom. If the unstructured covariance matrix results in convergence issue, the Fisher scoring algorithm may be used to obtain the initial values of covariance parameters. If convergence issues still cannot be resolved, a structured covariance matrix may be used with the heterogeneous Toeplitz covariance structure followed by the heterogeneous first-order autoregressive (AR[1]) structure. In the case that a structured covariance matrix needs to be used, a robust sandwich variance estimator will be used to address the potential adverse impact of covariance matrix misspecification. The difference between active dose and placebo at the endpoint visit will be estimated based on the least squares mean difference between the treatment groups at the endpoint visit from the MMRM with the associated 95% CI and p-values. The LS Mean (\pm SE) from the model will be plotted for change in PDSS total score during each visit by treatment group. Similarly, the mean (\pm SD) of absolute values and change from Baseline PDSS total score will be presented by visit and treatment group.

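### The PDSS mixed model holds the baseline slope constant over Days 42, 70 and 98; a baseline-by-visit term is a cheap safeguard in case that slope drifts

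*Protocol*

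**What the plan says.** Protocol 9.3.3.1 gives the fixed effects for change from baseline in PDSS total score: "An MMRM analysis will be used with fixed effect of treatment group, visits, evidence-based psychotherapy use, and interaction between treatment group and visit". SAP 5.12.1.2 lists the same four and then says "The baseline value of PDSS total score will be included as a covariate". SAP 5.5 names the covariates and adds no interaction. Both documents put an unconstrained covariance on the visits; the protocol wording is "An unstructured covariance structure will be used for the repeated measures".

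PDSS is measured after baseline at Days 42, 70 and 98 (Schedule of Assessments; SAP 4.3, Table 5). The estimand and the reported contrast are at Week 14 (Day 98) only.

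Protocol 9.3.4 extends the model: CGI-S, HAM-A, EQ-5D-5L and SDS "will be analyzed using similar MMRM models as described in" the PDSS section. SAP 5.15 does the same and includes the PDSS subscores.

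Three other SAP statements bear on the point. Section 1 says the SAP replaces the protocol's analyses. Section 5.12.1.1 uses data only up to the discontinuation visit. Section 5.13 lists no sensitivity analysis for PDSS, so the protocol's tipping-point analyses are gone.

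**The concern.** The outcome is a change score, so the baseline coefficient at a visit equals the slope of that visit's score on baseline, minus 1. If baseline predicts Day 98 less well than Day 42, that coefficient moves over time. The model estimates one value for all three visits, and the Week 14 contrast is then adjusted with a slope drawn partly from Days 42 and 70. Treatment and covariance are left free at each visit; baseline is held constant.

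Two things could follow at Week 14. Some residual variance that baseline could explain stays in the comparison. And if the baseline mix of those still observed differs between arms because of dropout, a wrong slope corrects for it wrongly. With data used only to discontinuation and no PDSS sensitivity analysis, the estimate leans on this mean model, and no other planned analysis would show the problem.

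**Working it through.** **The plan's own figure.** No power, SD or effect is stated for PDSS. The only sizing statement is for the primary endpoint: "A sample size of 114 participants per group (total of 228 participants) will provide at least 80% power", for "60% of darigabat group versus 40% of placebo group". With two-sided alpha 0.05 and 1:1 allocation, the two-proportion calculation gives 86.0% (83.8% for Fisher's exact test), so the stated bound holds. It says nothing about the PDSS model.

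**Assumed inputs for PDSS.** Baseline SD 3, 3.5 or 4.5 (entry at a total of 12 or more narrows the spread); residual SD 5 to 5.5, with 5.5 at Day 98; between-visit correlation 0.5-0.6 or 0.7-0.8; slopes on the change score centred on -0.5.

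**Precision, complete data.** Let b1, b2, b3 be the true slopes at the three visits. The single coefficient settles at the generalised least squares average b0 = (1'S⁻¹b)/(1'S⁻¹1), where S is the residual covariance. Relative to visit-specific slopes, the Week 14 variance is multiplied by

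1 + sx² (b3 - b0)² / S33

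where sx is the baseline SD and S33 the Day 98 residual variance.

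Worked case: residual SDs 5, 5.3 and 5.5, correlation 0.6 between adjacent visits and 0.5 between Days 42 and 98. The weights are 0.458, 0.254 and 0.288. For slopes -0.3/-0.5/-0.7, b0 = 0.458(-0.3) + 0.254(-0.5) + 0.288(-0.7) = -0.466. With sx = 3, the ratio is 1 + 9 × (-0.234)² / 30.25 = 1.0163, so the interval is √1.0163 - 1 = 0.81% wider.

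| Slopes at Days 42/70/98 | Drift per visit | Week 14 CI wider by |
|---|---|---|
| -0.5/-0.5/-0.5 | 0 | 0% |
| -0.4/-0.5/-0.6 | 0.1 | 0.2-0.6% |
| -0.3/-0.5/-0.7 | 0.2 | 0.8-2.3% |
| -0.2/-0.5/-0.8 | 0.3 | 1.8-5.0% |

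**With dropout.** The unstructured model was fitted with and without baseline-by-visit in 1,200 simulated trials of 114 per arm for SE and coverage, and in 8 runs of 20,000 per arm for bias. Baseline was truncated at 12 (SD about 3.3), the true effect was -2, and dropout by Day 98 was 17-34%. Drift of 0.2 per visit was not run here. Week 14 bias in PDSS points:

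| Dropout | Drift | One slope | With interaction |
|---|---|---|---|
| Unequal rates (34% vs 17%), unrelated to baseline | 0 to 0.3 | about -0.01 | about -0.01 |
| Depends on baseline or earlier scores, differently by arm | 0 | -0.01 to -0.02 | -0.01 to -0.02 |
| Same | 0.1 | +0.10 to +0.19 | -0.01 to -0.02 |
| Same | 0.3 | +0.31 to +0.57 | -0.01 to -0.02 |
| Depends on the unobserved score | 0 to 0.3 | +0.82 to +0.95 | about +0.82 |

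Values of -0.01 to -0.02 are simulation noise; a similar -0.016 appears with no dropout and flat slopes. Leaving aside the last row, coverage of the single-slope 95% interval stayed at 95-96%, except 92.7% in the worst case at drift 0.3. With dropout and flat slopes the interaction raised the SE by at most about 1.2% (0.836 against 0.826). At drift 0.1 it could still be slightly larger (0.836 against 0.829).

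**A second simulation** used total N of 120 and 228, about 60% observed at Week 14, and 350 trials per scenario. At drift 0.3 per visit (score slopes 0.9/0.6/0.3) and N = 120, the mean SE was 1.219 against 1.169, which is 4.3% in width. With dropout differing by arm, the single-slope estimate was further off by 0.214 - 0.030 = 0.18 points. The gap was 0.11 at drift 0.2, 0.07 at drift 0.1 and nil with constant slopes.

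**The case against.** A main-effect baseline covariate is an ordinary, prespecified form of this model, and nothing in the documents shows that the slope drifts. That stands: this is a refinement, not an error.

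The steepest pattern is also hard to believe. A score regressed on itself has slope 1 at Day -1. Score slopes of 0.9/0.6/0.3 would mean a fall of 0.1 over the first 43 days, then 0.3 in each following 28 days. That is 0.0107 against 0.0023 per day, over four times faster, whereas early response and regression to the mean after selection at 12 or more suggest that the larger fall comes first. So the small end of the range is the more plausible one. That also stands, as an inference.

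A reader might infer that unequal dropout by itself distorts Week 14. It does not: 34% against 17%, unrelated to baseline, gave no bias. Bias needs both a drifting slope and dropout tied to baseline or earlier scores differently by arm.

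A reader might also take the higher discontinuation expected in SAP Section 6 as evidence of such dropout. The SAP attributes it to the sponsor's closing of the trial, which gives no reason to expect a link to arm or baseline. It would thin the Day 98 data and so shift weight in the common slope to earlier visits, no more.

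Finally, the SAP drops the multiplicity hierarchy and calls efficacy exploratory, so a change of this size alters no confirmatory decision. What the objections leave untouched is that the term costs almost nothing and closes a route to bias that would otherwise go unseen.

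**Conclusion.** A cheap improvement of low severity. The single slope is confirmed in both documents, and the SAP text is the one to change. Whether it does harm depends on slope drift that the documents neither show nor rule out. The loss of precision is nil with constant slopes, at most about 2.3% of interval width up to a drift of 0.2 per visit, and about 5% at the extreme. The conditional bias of 0.1-0.2 points is 5-10% of an assumed 2-point effect; the extreme is about 0.6. In the scenarios run with a 2-point effect it was toward the null. All of this rests on assumed SDs, correlations, slopes and dropout.

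It would go too far to say that the planned model is invalid, that it necessarily widens the comparison, or that the added term repairs dropout bias in general. Under dropout driven by unobserved scores, at least about 0.8 points of bias remain either way.

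**What to change.** In SAP 5.12.1.2, add a baseline PDSS total score-by-visit interaction to the fixed effects. In SAP 5.15, for the other endpoints analysed with this model at more than one post-baseline visit, add the interaction of the planned baseline covariate with visit: PDSS subscores, CGI-S, HAM-A and SDS. EQ-5D-5L has one post-baseline visit and needs nothing. The Week 14 difference, interval and p-value are then obtained as planned. The change should be made before unblinding.

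Extra parameters equal the number of post-baseline visits minus one: two for PDSS (Days 42, 70, 98), three for CGI-S and HAM-A (Days 14, 42, 70, 98) and one for SDS (Days 42, 98). No new data are needed. The price is an SE up to about 1% larger if slopes are flat or nearly so. Dropout that depends on unobserved scores would need a separate sensitivity analysis.
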